6.4. Statistical analysis

6.4.1. General considerations

Statistical analyses will be performed using SAS® v9.4 or higher (SAS Institute, Cary NC, USA).

Baseline demographic and other baseline characteristics, together with safety analyses will be performed on all participants who underwent the treatment phase. Baseline values are defined as the last valid value prior to treatment.

Where confidence limits are appropriate, a two-sided 95% confidence interval will be constructed.

6.4.2. Demographic and other baseline variables

Demographic and baseline condition related characteristics will be tabulated. Continuous variables will be summarized by a mean, standard deviation, minimum, median and maximum, and categorical variables by a count and percentage.

Revision #: 1.0

Page: 17 of 20

6.4.3. Safety analysis

Safety and tolerability will be assessed by review of all safety parameters, including adverse events. Serious adverse events, device-related SAEs, adverse events (by type and overall), device-related AE, adverse device reactions and device malfunction rates will be documented. Treatment tolerability, the number and percent of subjects who fail to complete the study and the number and percent of subjects who fail to complete the study because of adverse events will be presented. Time to withdrawal will also be assessed and presented by Kaplan-Meier curves.

6.4.4. Efficacy analysis

The efficacy endpoints will be assessed on evaluable treatments of qualifying attacks. The first use of the device is considered a training treatment and will not be included in the efficacy analyses. The first treatment of a qualifying attack after the training treatment is considered a test treatment and will be used for all efficacy assessments. If this treatment is not evaluable (i.e., no pain data at 2 hours post-treatment), a subsequent treatment of a qualifying attack with evaluable data will be considered the test treatment.

Use of rescue medication before the 2-hours assessment will be considered a treatment failure for the 2-hours endpoints, and before the 24 hours assessment for the sustained 24-hours endpoints. The percentage of participants achieving each of the efficacy outcomes will be presented in a tabular form along with two-sided 95% exact confidence intervals.

For the associated symptoms outcomes, the observed response proportions and corresponding 95% exact confidence intervals for each associated symptom will be provided. All patients with baseline and 2 hours values will be included in the analyses. A response in each associated symptom (nausea, vomiting, photophobia, phonophobia) is defined as change from presence of a specific associated symptom at baseline to absence of the same associated symptom at 2 hours post-treatment.

In addition, logistic regression models will be used to assess the efficacy. Baseline value and site will serve as covariates.

The first secondary endpoint (pain relief at 2 hours) may also be evaluated in attacks with aura and attacks without aura separately.

7. Data management

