During the training, participants will also be informed on the key elements which are critical for the successful conduct of the study:

Revision #: 1.0 Page: 13 of 20

- Treatments of headache with Nerivio[™] should be performed within 60 minutes of awakening with a headache or upon increasing headache severity and always within one hour of symptoms onset. Treatments of mild headaches are accepted.
- Avoid taking rescue medications within two hours post-treatment (2 hours from start of treatment), if possible.

Revision #: 1.0

Page: 14 of 20

• The treatment should be performed for 45 minutes.

In addition, participants will complete study questionnaires, as required.

Phase 2 – Treatment phase: Participants will be instructed to use the device within 60 minutes of awakening with a headache or upon increasing headache severity during a period of 4 week. Participants will be instructed to use the device with the intensity level identified during the device training visit (with a range of ±5 units) and make sure the stimulation is perceptible but not painful. Participants will be instructed to avoid taking rescue medications within 2 hours post-treatment. If medications are used, participants will be instructed to record in the app when and which medication was taken. The participants will use the app to record pain intensity levels (none, mild, moderate, or severe) at baseline and 2 hours post-treatment, and to record the presence/absence of associated symptoms (nausea, photophobia, phonophobia) at baseline and 2 hours post-treatment.

Participants who do not achieve satisfactory relief at 2 hours post-treatment may treat again with the Nerivio[™] device or may treat with usual care at that time or any time thereafter if the headache does not resolve.

Third (final) visit – End of study: Participants will return to the clinic following the end of the 4-week treatment phase, at which time they will return the device and complete the required questionnaires

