5.3. Study endpoints

5.3.1. Primary endpoints

1. Pain relief at 2 hours post-treatment:

The proportion of participants achieving pain relief at 2 hours post-treatment in the test treatment, with no use of rescue/abortive medication (Pain relief defined as a reduction in pain scale from severe to moderate, mild, or none)from moderate or severe to mild or none.

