6.3. Analysis sets

Intent to treat analysis set (ITT)

The ITT analysis set includes all patients undergoing the treatment phase.

Modified intend to treat analysis set (mITT)

The mITT analysis set includes all patients undergoing the treatment phase and treat at least one (1) treatment within 60 minutes of headache onset. Subjects with no valid post baseline assessment will not be included in the relevant analysis.

Per-protocol analysis set (PP)

The PP analysis set includes all patients from the mITT analysis set without major protocol deviations. Main protocol instructions include:

- has started within 60 minutes of awakening with headache or increased intensity from baseline
 - was administered for 45 minutes
 - includes data on headache intensity at 2 hours post-treatment
 - rescue medication was not used before or within 2 hours post-treatment

Statistical analysis of the analysis sets

The ITT analysis set will serve as the main set for safety assessments.

The mITT analysis set will serve as the primary set for the efficacy assessment.

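### Section 6.4.4 does not say whether early rescue without a 2-hour score is a failure or a replaceable treatment, so a known non-response can be replaced by a later attack

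*Combined protocol and SAP*

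**What the plan says.** Section 6.4.4 limits the efficacy analysis to scored treatments: "The efficacy endpoints will be assessed on evaluable treatments of qualifying attacks". The first use of the device is training, and the first qualifying attack treated after it supplies the test treatment. The replacement rule follows: "If this treatment is not evaluable (i.e., no pain data at 2 hours post-treatment), a subsequent treatment of a qualifying attack" with usable data becomes the test treatment. Absence of 2-hour pain data is the only ground given for being non-evaluable, and it is introduced by i.e., so it reads as a definition and not as an example.

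The next paragraph of 6.4.4 gives the rescue rule: "Use of rescue medication before the 2-hours assessment will be considered a treatment failure for the 2-hours endpoints". It does not mention evaluability or replacement.

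Three other places bear on the point:

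- Section 5.3.1 builds rescue into the primary endpoint: relief must occur "in the test treatment, with no use of rescue/abortive medication".
- Section 6.3, on the mITT set, says: "Subjects with no valid post baseline assessment will not be included in the relevant analysis". It does not say whether recorded rescue counts as such an assessment.
- Section 5.2 discourages early rescue but does not forbid it: "Avoid taking rescue medications within two hours post-treatment (2 hours from start of treatment), if possible". It also asks participants to log in the app the drug taken and its time.

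**The concern.** A missing 2-hour score usually means that the outcome is unknown, and using a later attack is then a practical choice. Rescue before 2 hours is different. Under section 5.3.1 rescue alone makes the treatment a non-response, whatever the score would have been.

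Suppose a participant takes rescue medication at minute 60 and enters no 2-hour score. If the analyst first selects an evaluable treatment and then scores it, this treatment never becomes the test treatment. The rescue rule does not reach it, and the participant is judged on a later attack. If no later qualifying treatment is scored, the participant may drop out of the efficacy analysis under section 6.3.

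The primary result is a single-arm proportion, so no control arm offsets a shift of this kind. Two analysts could both follow 6.4.4 faithfully and report different primary results. In an open-label study that choice should be fixed before the data are seen.

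**Working it through.** **Inputs.** From the documents: up to 100 participants (sections 5.1 and 6.2) and two-sided 95% exact confidence intervals (6.4.4). The plan gives no rate of rescue, rate of missing scores, expected response rate or derivation of the sample size, so there is no figure of its own to reproduce. Everything below rests on stated assumptions.

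Let f be the share of participants whose first test treatment has rescue before 2 hours and no score, r the response rate on their replacement treatments, and p the response rate in the other participants.

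**Direction.** A rescued treatment counts 0 under 5.3.1. Its replacement counts 0 or 1. The rate cannot fall.

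**Size under replacement.**

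- Rescue counted as failure: (1 − f)p
- Treatment replaced: (1 − f)p + f × r
- Difference: f × r

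Difference in percentage points, for assumed f and r:

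| f | r = 20% | r = 30% | r = 60% |
|---|---|---|---|
| 0% | 0 | 0 | 0 |
| 1.5% | 0.3 | 0.45 | 0.9 |
| 5% | 1.0 | 1.5 | 3.0 |
| 10% | 2.0 | 3.0 | 6.0 |
| 15% | 3.0 | 4.5 | 9.0 |

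The 1.5% row is what 15% rescue and 10% missing scores would give if the two were independent (0.15 × 0.10 = 0.015). A participant who has given up on the device may well skip the score, and such dependence would make f larger.

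**Example.** Take 100 participants, f = 10% and 45 responders among the other 90 (p = 50%). Exact (Clopper-Pearson) 95% intervals:

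| Handling of the 10 | Result | 95% CI |
|---|---|---|
| Counted as failures | 45/100 = 45% | 35.0 to 55.3 |
| Replaced, r = 20% | 47/100 = 47% | 36.9 to 57.2 |
| Replaced, r = 30% | 48/100 = 48% | 37.9 to 58.2 |
| Replaced, r = 60% | 51/100 = 51% | 40.8 to 61.1 |

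**Limiting case of exclusion.** If none of the 10 has a later scored qualifying treatment, and recorded rescue is not taken as a valid assessment under 6.3, all 10 leave the analysis. The result is 45/90 = 50.0% (39.3 to 60.7). The difference is p − (1 − f)p = f × p = 0.10 × 50% = 5 points. Four weeks of treatment in participants with constant headache make this an extreme case.

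**The case against.** The strongest reply is that the rescue sentence in 6.4.4 carries no condition. It does not require a score, and 5.3.1 makes absence of rescue part of the response itself. An analyst may fairly apply that specific rule first and count the treatment as a failure, in which case nothing shifts. This stands. A reader might infer that the plan requires known failures to be discarded. The text does not support that: it permits the discard by leaving the order open.

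The second reply concerns frequency. The affected record needs early rescue and a missing score together. Participants are told to avoid early rescue, they enter the treatment phase only after at least 22 diary entries in the 28-day run-in, and rescue and pain scores go into the same app. The documents do not say whether a medication entry can exist without a 2-hour entry. This also stands, and it is why the range for f must start at zero.

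Third, the plan states no performance goal, null rate or success threshold for the primary proportion. The result is descriptive, with an interval of about 10 points either side at 100 participants, so no stated decision turns on the shift. That limits the consequence. It does not remove the point, because the shift is systematic and the interval makes no allowance for it.

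The per-protocol list in 6.3 names "includes data on headache intensity at 2 hours post-treatment" and "rescue medication was not used before or within 2 hours post-treatment" as separate conditions. A reader might take this as proof of how evaluability is meant to work in the mITT analysis. It concerns a different set and shows only that the plan distinguishes the two facts.

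**Conclusion.** The point holds as an unstated order between two rules that bear on the primary endpoint. Read in sequence, 6.4.4 lets a treatment that 5.3.1 already settles as a non-response be replaced by a later attack, and the primary rate can only rise or stay the same.

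The shift is f × r. With f assumed at 0% to 15% and r at 20% to 60%, it lies between 0 and about 9 points. It is zero if the rescue rule is applied first, if no such records occur, or if every replacement also fails. Neither input comes from the documents, so a reader should not infer that the reported rate will be inflated by any particular amount. The 45/90 exclusion result should be read only as a limit that needs every affected participant to lack a later scored qualifying treatment.

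The plan should be corrected before analysis. The size is unknown, but the direction is not, and the correction is small.

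**What to change.** In section 6.4.4, state:

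1. A test treatment with rescue medication taken within 2 hours of the start of treatment is evaluable and is a failure for the 2-hour endpoints, whether or not a 2-hour score exists. Timing goes by the recorded time of intake, whenever the entry was made, so that a dose taken at minute 60 and logged later is still counted.
2. Replacement by a later treatment applies only when there is neither a 2-hour score nor rescue taken within 2 hours.
3. The same failure rule applies to the 2-hour symptom and functional endpoints, and to each treated attack in the within-patient consistency endpoint.

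Item 3 is needed because 6.4.4 uses the test treatment for all efficacy assessments, while its symptom analysis takes only patients with baseline and 2-hour values. Without it, keeping a rescued, unscored treatment as the test treatment would drop the participant from the symptom results.

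In section 6.3, state that participants who fail under item 1 stay in the mITT efficacy analysis.

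The cost is a few sentences. No new procedure or larger sample is needed, since participants are already asked to log rescue use with its time. The sponsor should confirm that the app accepts a medication entry when no 2-hour score is given, because the rule depends on it. The downside is a slightly lower reported response rate, by f × r, or no change if these records are already counted as failures.

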
Revision #: 1.0

Page: 7 of 20

Within-patient consistency

The repeatability of headache reduction, as described in the primary endpoint definition, in subsequent treated attacks. Thus, this endpoint measures the % of patient responding to the primary endpoint in at least 50% of their treated attacks

Disappearance of associated symptoms at 2 hours post-treatment

Disappearance of nausea, photophobia and phonophobia at 2 hours post-treatment

Functional disability at 2 hours post-treatment

The proportion of participants achieving improvement of at least one grade in functional disability in the test treatment at 2 hours post-treatment with no use of rescue medication

Improve of quality of life

Reduction in average headache disability as measured by PedsMIDAS before and at 1 month after initiation of treatment with REN.

Revision #: 1.0 Page: 8 of 20

Exploratory endpoints	 Reduction in average headache intensity at 1 month after initiation of treatment with REN Reduction in perceived stress as it relates to headache, and adverse reactions experienced as measured by HIT-6.
Safety endpoints	 The safety of Nerivio The incidence of adverse events in general and by seriousness, severity and association to the device. Treatment tolerability The percent of subjects who fail to complete the study because of adverse events
Datasets	 Intent to treat analysis set (ITT) The ITT analysis set includes all participants undergoing the treatment phase. Modified intent to treat analysis set (mITT) The mITT analysis set includes all participants undergoing the treatment phase who treat a test treatment within 60 minutes of attack onset.
Data Analysis	The ITT analysis set will be used for the primary endpoints of safety and tolerability assessments. Safety assessments will include spontaneously reported adverse events. The mITT analysis set will be used for the efficacy assessments.

Revision #: 1.0

Page: 9 of 20

2. Background

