5.3.2. Secondary endpoints

1. Within-patient consistency

The repeatability of headache reduction, as described in the primary endpoint definition, in subsequent treated attacks. Thus, this endpoint measures the %

Revision #: 1.0

Page: 15 of 20

of patient responding to the primary endpoint in at least 50% of their treated attacks.

2. Disappearance of associated symptoms at 2 hours post-treatment

Disappearance of nausea, photophobia and phonophobia at 2 hours post-treatment.

3. Functional disability at 2 hours post-treatment

The proportion of participants achieving improvement of at least one grade in functional disability in the test treatment at 2 hours post-treatment with no use of rescue medication.

4. Improve of quality of life

Reduction in average headache disability as measured by PedsMIDAS before and at 1 month after initiation of treatment with REN.

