5.3.3. Exploratory endpoints

- 1. Reduction in average headache intensity at 1 month
- 2. Reduction in perceived stress

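### Section 6.4.4 reports every efficacy outcome as a percentage from one test treatment, but PedsMIDAS, average intensity and perceived stress/HIT-6 are score changes with no responder cut-off or change analysis, and consistency needs many attacks

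*Combined protocol and SAP*

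**What the plan says.** Section 6.4.4 (Efficacy analysis) gives a single reporting rule: "The percentage of participants achieving each of the efficacy outcomes will be presented in a tabular form along with two-sided 95% exact confidence intervals". It then adds logistic regression with baseline value and site as covariates. The first treatment of a qualifying attack after the training treatment is "considered a test treatment and will be used for all efficacy assessments".

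The endpoints that these rules must serve include:

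- Secondary endpoint 4 (section 5.3.2): "Reduction in average headache disability as measured by PedsMIDAS before and at 1 month after initiation of treatment with REN".
- Exploratory endpoint 1 (synopsis): "Reduction in average headache intensity at 1 month after initiation of treatment with REN". Section 5.3.3 has the shorter form "Reduction in average headache intensity at 1 month".
- Exploratory endpoint 2 (synopsis): "Reduction in perceived stress as it relates to headache, and adverse reactions experienced as measured by HIT-6". Section 5.3.3 has only "Reduction in perceived stress", with no instrument or time point.
- Secondary endpoint 1, within-patient consistency (section 5.3.2): the percentage "of patient responding to the primary endpoint in at least 50% of their treated attacks".

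Section 6.4.2 describes how continuous variables are summarised, but it covers demographic and other baseline variables. Section 6.4.1 says that confidence intervals, where appropriate, are two-sided 95%. It names no estimator for a change.

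**The concern.** A percentage with an exact interval and a logistic model both need a yes/no outcome for each participant. Elsewhere the plan supplies one: a category shift for pain relief, one grade for functional disability, half of the attacks for consistency, and present to absent for each symptom. For PedsMIDAS, average intensity and HIT-6 it supplies none, and it offers no analysis of the change itself.

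Two things are at stake. First, the cut-off that turns these scores into responses could be chosen after the data are seen, in an open-label single-arm study where a percentage has no control rate beside it. Second, the quantity that the endpoints describe, how far disability, intensity or stress falls, would not be estimated.

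The test-treatment sentence adds a separate mismatch. One treatment cannot show consistency across attacks, and the 1-month scores belong to no single treatment.

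**Working it through.** The plan gives no figure to reproduce. Section 6.2 states 100 participants without an effect size, SD, power or precision target. The check therefore has two parts.

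**1. Endpoints against the stated rules**

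| Endpoint | Responder rule given? | Obtainable from one test treatment? |
|---|---|---|
| Pain relief at 2 hours (primary) | Yes, category shift | Yes |
| Functional disability at 2 hours | Yes, one grade | Yes |
| Associated symptoms at 2 hours | Yes, present to absent | Yes |
| Within-patient consistency | Yes, 50% of attacks | No, needs many attacks |
| PedsMIDAS at 1 month | No | No |
| Average intensity at 1 month | No | No |
| Perceived stress/HIT-6 | No | No |

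Three endpoints lack a responder rule. Four cannot come from a single treatment.

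**2. What a percentage would mean if any fall were counted**

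This is one possible way to fill the gap, not a rule in the plan. The tie share, the SD of change and the drift are assumptions, because the documents give none.

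*No effect, symmetric change, tie share t.* P(fall) = (1 − t)/2.
- t = 0: 50%
- t = 0.1: 45%
- t = 0.2: 40%
- t = 0.4: 30%

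*No effect, whole-point score, normal change with SD s, rounded.* P(fall of at least 1 point) = Φ(−0.5/s).
- s = 2: Φ(−0.25) = 40%
- s = 5: Φ(−0.10) = 46%
- s = 10: Φ(−0.05) = 48%
- s = 20: Φ(−0.025) = 49%

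*No device effect, but a mean improvement of d SDs from regression to the mean or placebo response, no ties.* P(fall) = Φ(d).
- d = 0.2: 58%
- d = 0.25: 60%
- d = 0.5: 69%

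With no device effect, the percentage could thus lie anywhere from about 30% to 69% over these ranges. The exact interval does not help the reader place it: for 50 of 100 it runs from 39.8% to 60.2%, which measures sampling error only.

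*A cut-off moves the reference rate.* With a threshold of k SDs of change and no effect, P = Φ(−k): 31% at k = 0.5 and 16% at k = 1. The result depends on a number that the plan has not fixed.

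*Precision of the alternative.* A mean change has a 95% CI half-width of about 1.96/√n SDs. At n = 100 this is 1.96/10 = 0.196, or about 0.20 SD.

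**The case against.** The strongest reply is that the percentage sentence was never meant for these endpoints. Section 6.4.4 opens by tying efficacy to treated attacks, the sentence follows the rescue-medication rules for 2-hour and 24-hour outcomes, and its verb matches the responder endpoints. On that reading the three scores simply have no stated analysis, and no misleading table would be produced. This reading is possible, but it has to override the words *each* and *all* in the two sentences. It also leaves the gap open: no change analysis appears anywhere, and section 6.4.2 is confined to baseline. Likewise, the specific definition of consistency may be taken to override the general test-treatment sentence, but the text should say so.

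A reader might go further and infer that the plan counts any 1-point fall as a response, so that half of the participants respond with no effect. The documents do not support that.

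- No section says that a 1-point fall, or any fall, is a response. The response is undefined.
- The 50% needs a symmetric change and few ties.
- A 1-point rule does not suit average intensity, which is recorded in four categories. With 0–3 coding (assumed), a 1-point fall in the average is a whole category. For an assumed SD of change of 0.3, 0.5 or 0.7, Φ(−1/SD) gives 0.04%, 2.3% or 7.7% under no effect.

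It is also tempting to quantify lost power against a paired test. That would need an effect size and a null proportion, and the plan states neither, so I make no such claim.

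One further objection stands in full: in a single-arm study a mean change also contains regression to the mean and placebo response. Changing the summary does not remove them.

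**Conclusion.** The point holds as a mismatch between the stated efficacy rules and four listed endpoints. Three of them (one secondary, two exploratory) have neither a responder threshold nor a change-from-baseline analysis. The fourth, consistency, has a definition but conflicts with the test-treatment sentence. This part rests on the text alone and needs no assumption.

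The numerical consequence is conditional. Only if any fall were counted would the no-effect percentage be 30% to 50% (ties from 40% to none, symmetric change), or 58% to 69% with an assumed drift of 0.2 to 0.5 SD. The width of that range is the difficulty: the reader could not tell what percentage to expect without a device effect.

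The primary endpoint and the other 2-hour responder endpoints are not touched. The change should be made before analysis, but it does not bear on the trial's main conclusion.

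**What to change.** 1. In section 6.4.4, limit the percentage, exact-interval and logistic rules to the 2-hour responder endpoints and within-patient consistency.
2. For PedsMIDAS, average headache intensity and HIT-6, report within-participant change from baseline as mean and median with a two-sided 95% CI: paired t, or signed-rank with a Hodges–Lehmann interval if the changes are skewed. Add a responder percentage only with a cut-off fixed and justified beforehand.
3. Reword the test-treatment sentence so that it covers only the 2-hour endpoints, and state that consistency uses all evaluable treated attacks.
4. Carry HIT-6 and its time point from the synopsis into section 5.3.3, and confirm that each questionnaire is completed at both visits needed for a change. Section 5.2 refers to questionnaires without naming them.
5. Describe the reported changes as uncontrolled pre–post differences that include regression to the mean and placebo response.

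The cost is SAP wording and a little more analysis. No new data should be needed, provided the questionnaires in item 4 are indeed collected at both times.
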